9.5.1.2 Efficacy Assessments

Tumor assessments will be performed using RECIST 1.1 (Appendix 8). Investigator-determined response assessments will be performed at each assessment time point and entered onto the case report form (CRF). Copies of all tumor assessment scans will be sent to an ICL designated by the sponsor for blinded independent efficacy assessment until the data cutoff for the primary analysis. For subjects enrolled after implementation of Amendment 06, tumor assessments will be carried out following the guidelines provided by the ICL.

Tumor assessments (computed tomography [CT] chest, and CT or MRI abdomen, pelvis, and other known or suspected sites of disease) will be performed during the Prerandomization Phase and then, during the Randomization Phase, every 8 weeks (within the 8th week) until documentation of progressive disease as determined by the investigator and on a schedule as determined by the treating physician after the data cutoff for the primary analysis, but not less frequently than every 12 weeks or earlier if clinically indicated. Historical CT or MRI scans performed within 28 days of randomization but before informed consent may be used as screening scans provided they meet minimum standards as separately defined by the ICL. The same imaging modality and image-acquisition protocol (including use or nonuse of contrast) should be used consistently across all time points. All responses must be confirmed no less than 4 weeks following the initial indication of response. A chest x-ray or a skeletal x-ray that clearly demonstrates a new metastatic lesion may be used to document progression in lieu of the CT/MRI scans.

A bone scan (^{99m}m-technetium-based scintigraphy, whole-body bone MRI, or ¹⁸F-sodium fluoride positron emission tomography [NaF PET]) will be performed during the Prerandomization Phase to establish a baseline (a historical bone scan performed within 6 weeks prior to randomization is acceptable), every 24 weeks after randomization, within a

target of 1 week but no more than 2 weeks following a complete response (CR) as assessed by the investigator, and as clinically indicated after the data cutoff for the primary analysis. Lesions identified on bone scans should be followed at all tumor assessment time points with cross-sectional imaging.

A brain scan will be performed at screening and as clinically indicated thereafter, and within a target of 1 week but no more than 2 weeks following achievement of a confirmed CR. For subjects with a history of protocol-eligible treated brain metastases, a brain scan will be required at all protocol-specified tumor assessment time points (eg, every 8 weeks). Subjects with protocol-eligible treated brain metastases should also have brain CT/MRI performed as per local standard of care. For other subjects, brain scans should be performed as clinically indicated.

Stable disease must be achieved at ≥ 7 weeks after randomization to be considered best overall response. Subjects going off treatment without disease progression in the Treatment Period will continue to undergo tumor assessments in the Follow-up Period per the above schedule until disease progression is documented, another anticancer therapy is initiated, or data cutoff for the primary analysis.

9.5.1.3 Pharmacokinetic, Pharmacodynamic, and Other Biomarker Assessments

9.5.1.3.1 PHARMACOKINETIC ASSESSMENTS

Sparse PK samples (plasma for lenvatinib and whole blood for everolimus) will be collected from all subjects and will be analyzed using a population PK approach (PopPK). The timing for obtaining the 7 PK sampling time points (one tube each for lenvatinib and everolimus PK) is shown in the Schedule of Procedures/Assessments (Table 6) and Table 4. See the Laboratory Manual for a description of collection, handling, and shipping procedures for PK samples. A separate statistical analysis plan will be developed for the PopPK analysis.

Table 4 Pharmacokinetic Sampling Time Points

Time Point	Sample Number	Time (h)
Cycle 1/Day 1	1	0.5-4 h postdose
	2	6-10 h postdose
Cycle 1/Day 15 ^a	3	Predose on Day 15 (Cycle 1)
	4	0.5-4 h postdose
	5	6-10 h postdose
Cycle 2 Day 1	6	Predose on Day 1 (Cycle 2)
	7	2-12 h postdose

h = hour(s).

a If dose interruption is necessary in these time points, only predose sample should be collected.

9.5.1.3.2 PHARMACODYNAMIC AND OTHER BIOMARKER ASSESSMENTS

Pharmacodynamic and Other Biomarker Assessments

Blood samples will be collected for peripheral blood mononuclear cell (PBMC) and plasma isolation from all study subjects at protocol specified time points, during the Randomization Phase of the study, as indicated in the Schedule of Procedures/Assessments (Table 6). There will be no further biomarker sample collection after the data cutoff for the primary analysis. Biomarker discovery or validation will be performed to identify blood biomarkers that may be useful to measure subject response to study drug, to understand the underlying disease biology, to provide further insight into the mechanism of action of the study drug as well as for potential use in diagnostic development.

These samples may undergo enzyme-linked immunosorbent assay (ELISA), multiplex bead-based immunoassay and/or other appropriate analysis procedures to explore blood biomarkers (eg, VEGF, Ang-2). In addition, other pharmacodynamics target engagement and response biomarkers related to study drug may be assessed. See Appendix 12 for description of sample collection and handling, procedures for securing and retention of samples, and subject privacy information).

Instructions for the processing, storage, and shipping of samples will be provided in the Laboratory Manual (see also Appendix 12).

9.5.1.4 Safety Assessments

Safety assessments will consist of monitoring and recording all AEs, including all CTCAE v4.03 grades (for both increasing and decreasing severity) and SAEs; regular monitoring of hematology, blood chemistry, and urine values; periodic measurement of vital signs and electrocardiograms (ECGs); and performance of physical examinations during the Randomization Phase. An echocardiogram or a MUGA scan including LVEF will be performed at screening, and as clinically indicated. After the data cutoff for the primary analysis, all AEs leading to study discontinuation, SAEs and concomitant medications will be monitored and recorded. Hematology and blood chemistry will be monitored prior to administration of study drug and as clinically indicated. Urine dipstick testing will be monitored at each visit and as clinically indicated. A serum or urine pregnancy test will be performed during the study for women of childbearing potential. A symptom-directed physical examination and vital signs (resting BP, HR, RR and body temperature) will be performed at each visit and as clinically indicated. A 12-lead ECG and Echocardiogram/MUCA scan will be performed as clinically indicated (Table 7).

Progression of RCC and signs and symptoms clearly related to the progression of RCC should not be captured as an AE. Disease progression is a study endpoint and should be captured in the CRF as per the guidelines for reporting disease progression.

9.5.1.4.1 ADVERSE EVENTS AND EVENTS ASSOCIATED WITH SPECIAL SITUATIONS

An AE is any untoward medical occurrence in a patient or clinical investigation subject administered an investigational product. An AE does not necessarily have a causal relationship with the medicinal product. For this study, the study drugs are lenvatinib and everolimus.

The criteria for identifying AEs in this study are:

- Any unfavorable and unintended sign (including an abnormal laboratory finding), symptom, or disease temporally associated with the use of an investigational product, whether or not considered related to the investigational product (Note: Every sign or symptom should not be listed as a separate AE if the applicable disease [diagnosis] is being reported as an AE)
- Any new disease or exacerbation of an existing disease. However, worsening of the primary disease should be captured under efficacy assessments as disease progression rather than as an AE
- Any deterioration in nonprotocol-required measurements of a laboratory value or other clinical test (eg, ECG or x-ray) that results in symptoms, a change in treatment, or discontinuation of study drug
- Recurrence of an intermittent medical condition (eg, headache) not present pretreatment (Baseline)
- An abnormal laboratory test result should be considered an AE if the identified laboratory abnormality leads to any type of intervention, withdrawal of study drug, or withholding of study drug, whether prescribed in the protocol or not

All AEs observed during the study will be reported on the CRF. All AEs, regardless of relationship to study drug or procedure, should be collected beginning from the time the subject signs the study ICF through the last visit. Subjects who fail screening primarily due to AE(s) must have the AE(s) leading to screen failure reported on the Screening Disposition CRF. All AEs and SAEs will be collected for 28 days after the last dose.

After the data cutoff for the primary analysis, all AEs leading to study drug discontinuation and SAEs will be recorded until 28 days after the last dose of study drug. SAEs, irrespective of relationship to study drug, must be reported as soon as possible but not later than 24 hours from the date when the investigator becomes aware of the event.

Abnormal laboratory values should not be listed as separate AEs if they are considered to be part of the clinical syndrome that is being reported as an AE. It is the responsibility of the investigator to review all laboratory findings in all subjects and determine if they constitute an AE. Medical and scientific judgment should be exercised in deciding whether an isolated laboratory abnormality should be classified as an AE. Any laboratory abnormality considered to constitute an AE should be reported on the Adverse Event CRF.

Abnormal ECG (QTc) results, if not otherwise considered part of a clinical symptom that is being reported as an AE, should be considered an AE if the QTc interval is more than 450 ms and there is an increase of more than 60 ms from baseline. Any ECG abnormality that the investigator considers as an AE should be reported as such.

All AEs must be followed for 28 days after the subject's last dose, or until resolution, whichever comes first. Subjects with onset of an AE or deterioration of a preexisting AE will be followed until resolution to baseline, start of a new anticancer treatment, or death. All SAEs must be followed to resolution or, if resolution is unlikely, to stabilization.

Every effort must be made by the investigator to categorize each AE according to its severity and its relationship to the study treatment.

Assessing Severity of Adverse Events

Adverse events will be graded on a 5-point scale according to CTCAE v4.03 ([Appendix 3](#)). Investigators will report CTCAE grades for all AEs (for both increasing and decreasing severity). For Grade 2 AEs that lead to changes in study drug administration (dose held, dose reduced, or dosing discontinuation), the investigator will be required to confirm in the CRF that the AE is considered intolerable.

Assessing Relationship to Study Treatment

Items to be considered when assessing the relationship of an AE to the study treatment are:

- Temporal relationship of the onset of the event to the initiation of the study treatment
- The course of the event, especially the effect of discontinuation of study treatment or reintroduction of study treatment, as applicable
- Whether the event is known to be associated with the study treatment or with other similar treatments
- The presence of risk factors in the study subject known to increase the occurrence of the event
- The presence of non-study treatment-related factors that are known to be associated with the occurrence of the event

Classification of Causality

The relationship of each AE to the study drug will be recorded on the CRF in response to the following question:

Is there a reasonable possibility that the study drug caused the AE?

Yes (related) A causal relationship between the study drug and the AE is a reasonable possibility.

No (not related) A causal relationship between the study drug and the AE is not a reasonable possibility.

9.5.1.4.2 SERIOUS ADVERSE EVENTS AND EVENTS ASSOCIATED WITH SPECIAL SITUATIONS

A serious adverse event (SAE) is any untoward medical occurrence that at any dose:

- Results in death
- Is life-threatening (ie, the subject was at immediate risk of death from the adverse event as it occurred; this does not include an event that, had it occurred in a more severe form or was allowed to continue, might have caused death)
- Requires inpatient hospitalization or prolongation of existing hospitalization

- Results in persistent or significant disability/incapacity
- Is a congenital anomaly/birth defect (in the child of a subject who was exposed to the study drug)

Other important medical events that may not be immediately life-threatening or result in death or hospitalization but, when based on appropriate medical judgment, may jeopardize the subject or may require intervention to prevent one of the outcomes in the definition of SAE listed above should also be considered SAEs. Medical and scientific judgment should be exercised in deciding whether expedited reporting is appropriate in such situations.

In addition to the above, events associated with special situations include pregnancy or exposure to study drug through breastfeeding; AEs associated with study drug overdose, misuse, abuse, or medication error. These events associated with special situations are to be captured using the SAE procedures but are to be considered as SAEs only if they meet one of the above criteria. All AEs associated with special situations are to be reported on the CRF whether or not they meet the criteria for SAEs.

All SAEs must be followed to resolution or, if resolution is unlikely, to stabilization.

The following hospitalizations are not considered to be SAEs because there is no “adverse event” (ie, there is no untoward medical occurrence) associated with the hospitalization:

- Hospitalizations for respite care
- Planned hospitalizations required by the protocol
- Hospitalization planned before informed consent (where the condition requiring the hospitalization has not changed after study drug administration)
- Hospitalization for administration of study drug or insertion of access for administration of study drug
- Hospitalization for routine maintenance of a device (eg, battery replacement) that was in place before study entry

If possible, a blood sample for the measurement of study drug plasma concentration should be drawn at the first report of an SAE or a severe unexpected AE and at its resolution. A blood sample to measure study drug plasma concentrations will no longer be needed after the data cutoff for the primary analysis.

9.5.1.4.3 LABORATORY MEASUREMENTS

Clinical laboratory tests to be performed, including hematology, chemistry, urine dipstick testing, and a serum or urine pregnancy test (for female subjects of childbearing potential), are summarized in [Table 5](#). Subjects should be in a seated or supine position during blood collection. The Schedule of Procedures/Assessments ([Table 6](#)) and the Schedule of Assessments After the Data Cutoff for the Primary Analysis ([Table 7](#)) shows the visits and time points at which blood for clinical laboratory tests and urine for dipstick testing (and possible 24-hour urine collection to quantify the 24-hour urine protein excretion) will be collected in the study.

Clinical laboratory tests during the Randomization Phase of the study will be performed by a central laboratory. All blood and urine samples (except urine sample for urine dipstick) will be collected and sent to the central laboratory on the day of collection unless otherwise instructed. In cases of a safety concern or to guide clinical dosing, a local laboratory may be used in addition to the central laboratory testing. If central laboratory results are not available within the necessary timeframe to allow the subject to be enrolled, local laboratories will perform tests to qualify subjects for entry into the study. Laboratory certification as available will be included in the final clinical study report for this study. After the data cutoff for the primary analysis, clinical laboratory tests can be performed by the local laboratory and samples will no longer be sent to the central laboratory.

Urine dipstick testing will be performed, preferably at the investigational site (but may be performed locally by the primary care physician or a local laboratory if the subject does not have to come for a visit to the site).

Table 5 Clinical Laboratory Tests

Category	Parameters
Hematology	Hematocrit, hemoglobin, platelets, RBC count, and WBC count with automated differential (including absolute neutrophil count and absolute lymphocyte count) INR ^a
Chemistry	
Electrolytes	Bicarbonate, calcium, chloride, magnesium, phosphorous, potassium, sodium
Liver function tests	Alanine aminotransferase, alkaline phosphatase, aspartate aminotransferase, direct bilirubin, total bilirubin
Renal function tests	Blood urea/blood urea nitrogen, creatinine
Thyroid function tests ^b	Thyroid stimulating hormone, free T4 level
Other	Albumin, cholesterol, glucose ^c , lactate dehydrogenase, total protein, triglycerides, amylase, lipase, creatine kinase Serum or urine pregnancy test ^d (β-hCG or hCG)
Urine Dipstick Testing ^e	glucose, hemoglobin (or blood), ketones, pH, protein ^f , specific gravity

Category	Parameters
RBC = red blood cell, WBC = white blood cell, INR = International Normalized Ratio.	

 a. INR should only be performed as part of the screening assessment and when clinically indicated. b. Free T4 and TSH levels will be performed at the Screening Visit, at the Baseline Visit (or within 72 hours prior to the first dose of study drug). TSH levels will be repeated at Day 1 of every other cycle (starting with Cycle 2) and at the Off-Treatment visit. c. For subjects with blood glucose >ULN, a fasting (>6 h, water only) blood glucose sample will be obtained. d. For women of childbearing potential (ie, premenopausal women and postmenopausal women who have been amenorrheic for less than 12 months) e. If urine dipstick testing suggests a urinary tract infection, a urinalysis with microscopy and/or urine culture with sensitivities should be considered, if clinically indicated, at the institution's laboratory. f. If urine protein by dipstick is $\geq 2+$ (first occurrence or a subsequent increase in severity of urine dipstick proteinuria occurring on the same lenvatinib dose level), then a 24-hour urine collection should be done to quantify the 24-hour urine protein excretion. 	

All hematology, clinical chemistry (including pregnancy test, as applicable), and urine samples are to be obtained prior to study drug administration and results reviewed prior to administration/dispensing of study drug at the beginning of Cycle 1, and within 48 hours of Day 1 in each treatment cycle and within 72 hours of Day 1 after the data cutoff for the primary analysis. Refer to [Table 2](#) for management of clinically significant laboratory abnormalities.

A laboratory abnormality may meet the criteria to qualify as an AE as described in this protocol (see [Section 9.5.1.4.1](#) and the CRF Completion Guidelines. In these instances, the AE corresponding to the laboratory abnormality will be recorded on the Adverse Event CRF.

9.5.1.4.4 VITAL SIGNS AND WEIGHT MEASUREMENTS

Vital sign measurements (ie, systolic and diastolic BP [mmHg], pulse [beats per minute], respiratory rate [per minute], body temperature [in centigrade]), and weight (kg) will be obtained at the visits designated in the Schedule of Procedures/Assessments ([Table 6](#)) by a validated method. Blood pressure and pulse will be measured after the subject has been resting for 5 minutes. All BP measurements should be performed on the same arm, preferably by the same person. One BP assessment is defined as the mean value of 3 measurements at least 5 minutes apart. After the data cutoff for the primary analysis, one BP assessment is defined as the mean value of 2 measurements at least 5 minutes apart.

Vital sign measurements (resting BP [including date and time of measurement], HR, RR and body temperature) will be obtained, excluding weight at the visits designated in the Schedule of Assessments After the Data Cutoff for the Primary Analysis ([Table 7](#)).

For subjects with an elevated BP (systolic BP ≥ 140 mm Hg or diastolic BP ≥ 90 mmHg), confirmation should be obtained by performing 2 assessments a minimum of 30 minutes apart.

Subjects with systolic BP ≥ 160 mmHg or diastolic BP ≥ 100 mmHg must have their BP monitored every 2 weeks (on Day 1 and Day 15 or more frequently, as clinically indicated) until systolic BP has been ≤ 150 mmHg and diastolic BP has been ≤ 95 mmHg for 1 treatment cycle (ie, 56-day cycle). A diary will be provided to the subject to capture the BP evaluations between study visits. See subsection for management of hypertensive subjects ([Section 9.4.2.2](#)).

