- e. Assessments will include vital signs (resting BP [including date and time of measurement], HR, RR and body temperature), weight, and height. Height will be measured at the Screening visit only. One BP assessment is defined as the mean value of 3 measurements at least 5 minutes apart. An elevated BP assessment (ie, systolic BP ≥140 mmHg or diastolic BP ≥90 mmHg) should be confirmed by a repeat assessment after a minimum of 1 hour. Subjects with systolic BP ≥160 mmHg or diastolic BP ≥100 mmHg must have their BP monitored every 2 weeks (on Day 1 and Day 15 or more frequently, as clinically indicated) until systolic BP has been ≤150 mmHg and diastolic BP has been ≤95 mmHg for 3 consecutive months. A diary will be provided to the subject to capture the blood pressure evaluations between study visits. See subsection for [management of hypertensive subjects](#).
Note: During Cycle 3 and subsequent cycles, subjects may return to the clinic for the Day 15 visit if BP monitoring testing is required as specified above. The Day-15 visit is mandatory in Cycles 1 and 2.
- f. A comprehensive physical examination (including a neurological examination) will be performed at the Screening or Baseline Visits, on Cycle 1/Day 15, on Day 1 of each subsequent cycle, and at the Off-Treatment assessment. A symptom-directed physical examination will be performed on C1D1

and at any time during the study, as clinically indicated.

- g. Required if screening physical examination was performed >7 days prior to C1D1.
- h. Single 12-lead ECG. Subjects are suggested to be in the recumbent position for a period of 5 minutes prior to obtaining ECG.
- i. An echocardiogram or MUGA scan to assess LVEF will be performed at Screening and as clinically indicated.
- j. A serum or urine pregnancy test will be performed at the Screening Visit, at the Baseline Visit (or within 72 hours prior to the first dose of study drug), at Day 1 of every cycle (starting with Cycle 2), and at the Off-Treatment assessment in women of childbearing potential (ie, premenopausal and perimenopausal women who have been amenorrheic for less than 12 months).

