5.6.5 Vital Signs

Descriptive statistics for vital sign parameters (systolic and diastolic blood pressure, pulse, respiratory rate, temperature, and weight) and changes from baseline at each scheduled visit will be presented.

Blood pressure will also be summarized using a shift table from baseline to worst postbaseline CTCAE grade by the categories defined in [Table 8](#) below based on CTCAE grades.

Table 8 Blood Pressure Grades

Grade	Blood Pressure (mm Hg)	
	Systolic	Diastolic
0 (Normal)	≤119	≤79
1 (Prehypertension)	120–139	80–89
2 (Stage 1 Hypertension)	140–159	90–99
3 (Stage 2 Hypertension)	≥160	≥100

Subjects with systolic blood pressure ≥ 140 mm Hg or diastolic blood pressure ≥ 90 mm Hg during treatment will be listed along with their hypertensive medications.

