8 DEFINITIONS AND CONVENTIONS FOR DATA HANDLING

8.1 Visit Windows

Visit windows will be defined to be upper and lower bounds of 3 days of the scheduled visit, following the protocol, which states that efforts should be made to conduct study visits (and safety assessments) on the day scheduled (± 3 days).

Tumor assessments are to be performed every 8 weeks (during the 8th week, starting from the date of randomization), or sooner if clinically indicated, until progressive disease during Randomization Phase. If a subject discontinues from study treatment without disease progression, tumor assessments should continue to be performed every 8 weeks until documentation of disease progression or beginning a new anticancer treatment during Follow-up Period.

In the calculation of descriptive statistics for laboratory values and vital signs, if a visit has multiple observations, the observation closest in date and time to the target visit day will be used in the analysis. If two or more observations have the same distance to the target visit day, the one that has the highest CTCAE grade or is furthest away from the normal range will be used.

The purpose of this windowing is to provide a single record per subject per visit for the calculation of descriptive statistics per scheduled visit, and change from baseline per visit. Other safety analyses (eg, worst grade laboratory results and shift tables) will include all postbaseline assessments, including those scheduled and unscheduled visits.

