8.2 Baseline Definitions

For safety assessments, the baseline value is defined as the last non-missing measurement taken on or prior to the first dose date. The first dose date is defined as the earliest date of non-zero dose administration of either study drug (ie, lenvatinib or everolimus).

Study day is defined as date of assessment – first dosing date + 1 for any assessment done on or after first dosing date; otherwise, study day is defined as date of assessment – first dosing date.

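### Confirmatory BP repeats meet different selection rules at baseline (SAP 8.2) and on treatment (SAP 8.1), which pushes the descriptive mean BP change upward

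*Protocol*

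**What the plan says.** - **Trigger for the repeat.** Protocol 9.5.1.4.4: for systolic BP of at least 140 or diastolic of at least 90 mmHg, "confirmation should be obtained by performing 2 assessments a minimum of 30 minutes" apart. Table 6, footnote e, has the same trigger but another interval: an elevated assessment "should be confirmed by a repeat assessment after a minimum of 1 hour". Protocol 9.4.2.2 also uses 30 minutes.
- **What is recorded.** "One BP assessment is defined as the mean value of 3 measurements at least 5 minutes apart" during the Randomization Phase. Table 6, footnote e, asks for the date and time of each measurement.
- **By-visit values.** SAP 8.1, for laboratory values and vital signs, first takes the observation nearest in date and time to the target visit day. Then: "If two or more observations have the same distance to the target visit day, the one that has the highest CTCAE grade" or lies furthest outside the normal range is used.
- **Baseline.** SAP 8.2: "the baseline value is defined as the last non-missing measurement taken on or prior to the first dose date".
- **Worst-grade tables.** SAP 5.6.5: "Blood pressure will also be summarized using a shift table from baseline to worst postbaseline CTCAE grade". SAP 8.1: "Other safety analyses (eg, worst grade laboratory results and shift tables) will include all postbaseline assessments", from scheduled and unscheduled visits.

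Neither document says how a confirmatory repeat enters the analysis.

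**The concern.** The repeat is one-sided. A low first assessment stands alone; a high one gets a second. A first assessment that crosses 140 mmHg partly by chance tends to be followed by a lower one. A rule that keeps the repeat lets this regression to the mean operate, and a rule that keeps the higher of the two blocks it.

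The SAP appears to do the first at baseline and the second on treatment. The two ends of the change score are then selected in opposite directions, and part of the tabulated rise would come from the selection rule and not from the drug. Protocol 9.4.2.2 names hypertension as a recognized effect of this drug class, so readers will look at these tables.

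**Working it through.** **No figure to reproduce.** The documents give no BP mean, SD, repeat rate or expected change. The size below rests on assumptions; the direction follows from the rules.

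**Step 1: do the two assessments tie?** SAP 8.1 measures distance to a target visit day, which has no clock time. Two assessments 30 minutes or 1 hour apart will usually share a date. Counted in days they tie, and the worse is used. If recorded time breaks the tie, one of the two is kept, and the SAP does not say which.

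**Step 2: set-up (assumed).** Systolic BP only. True value T is normal with mean 130 and between-subject SD 12 mmHg. First assessment a and repeat b are each T plus independent error with SD s. The repeat is taken only if a is at least 140. True change is zero. Baseline keeps the last value, as in SAP 8.2.

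**Step 3: formulas for the spurious change.**
- On treatment keeps the first reading: the excess is the mean of (a − b) over subjects with a ≥ 140, counting others as 0. This equals (s²/S) × φ(10/S), where S = √(144 + s²) and φ is the standard normal density.
- On treatment keeps the higher reading: the excess is the mean of max(a − b, 0), counted the same way. This was simulated (200,000 subjects for SDs 4 to 10, with SD 3 run the same way).
- Both ends use the mean of the pair, or both use the last value: the excess is 0 by symmetry.

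Worked case, s = 6: S = √180 = 13.42; 10/S = 0.745; φ = 0.302; (36/13.42) × 0.302 = 0.81 mmHg. The simulation also gives 0.81.

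| Assessment SD (mmHg) | Higher on treatment, last at baseline | First on treatment, last at baseline | Mean of pair at both |
|---|---|---|---|
| 3 | +0.5 | +0.2 | 0.0 |
| 4 | +0.7 | +0.4 | 0.0 |
| 6 | +1.2 | +0.8 | 0.0 |
| 8 | +1.9 | +1.4 | 0.0 |
| 10 | +2.7 | +2.1 | 0.0 |

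**Step 4: a real rise.** With a true rise of 8 mmHg and SDs of 4 to 10, the higher-versus-last rule reports 9.1 to 11.3. The mean of the pair at both ends reports 7.7 to 7.9.

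**Step 5: arm difference.** With true rises of 8 and 5 mmHg, the true difference of 3.0 is reported as 3.2 to 3.4 (SDs 4 to 10). The bias is nearly equal in the two arms and largely cancels.

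**Step 6: worst grade.** Over 10 visits, with a true rise of 8 mmHg and an assumed visit-to-visit SD of 5, worst systolic BP of at least 160 occurs in 20% to 43% of subjects on any reading, and in 12% to 16% when both readings must support it. This compares two rules; neither is the true rate.

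**The case against.** - **The worse value is only a tie-break.** SAP 8.1 looks first for the nearest observation in date and time, and BP times are recorded ("resting BP [including date and time of measurement"]). A reader might infer that a normal repeat can never count on treatment. The text does not establish that. This stands as a limit on the claim, but it does not remove the problem: keeping the first reading still leaves +0.2 to +2.1 mmHg. Only keeping the last reading on treatment would remove it, and the SAP does not say so.
- **Same-day repeats and separate records are inferred.** The protocol sets minimum intervals only, and derivation rules sit in separate specifications (SAP 9). This stands as a stated assumption.
- **The upper SDs are generous.** Each assessment is already a mean of 3. With independent errors, an assessment SD of 8 implies 8 × √3 = 13.9 mmHg per measurement, and 10 implies 17.3. The check also leaves out antihypertensive treatment and the 150/90 mmHg limit at Screening, which would make high baseline readings rarer. The lower rows of the bias range are therefore the safer guide.
- **A worst-value table should use every assessment.** This stands. It is normal practice for a safety table, and the protocol attaches confirmation to the management of BP, not to its tabulation. Grading by the lower of the pair would select downward, so it should not replace the planned table.

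**Conclusion.** The point holds as a limited defect in descriptive tables. The SAP selects one value from a BP pair differently at baseline and on treatment, and the pair exists only when the first reading was high. If repeats are same-day and stored separately, mean systolic change is overstated by about 0.5 to 2.7 mmHg at zero true change (assumed assessment SDs 3 to 10), or by 0.2 to 2.1 mmHg if time favours the first reading.

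Three stronger readings are not supported:
- *Hypertension grades or the primary safety endpoint are inflated.* Protocol 9.5.1.4.1 has investigators report CTCAE grades for adverse events. SAP 8.1 does not derive them, so the endpoint in SAP 5.6.1 is untouched.
- *The comparison of starting doses is distorted.* For mean change, 3.0 mmHg becomes 3.2 to 3.4, which is small.
- *The Table 8 shift table is wrong because it counts unconfirmed readings.* It does what a worst-value table is meant to do. A confirmed version would add information, but it is not a correction.

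Separately, the 30-minute and 1-hour repeat intervals contradict each other whatever is decided on the analysis.

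**What to change.** 1. In SAP 8.1 and 8.2, exempt BP from the worst-of-ties rule. Where an elevated assessment has its protocol repeat, use the mean of the first and repeat assessments, for baseline and by-visit values alike.
2. In SAP 5.6.5, keep the Table 8 worst-grade shift table on all assessments, and add a supplementary version restricted to confirmed elevations.
3. Reconcile the repeat interval in Protocol 9.5.1.4.4 and 9.4.2.2 (30 minutes) with Table 6, footnote e (1 hour). Which one applies is for the sponsor to settle.

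The cost is a few sentences in the SAP, a small programming change and one extra table. BP is already collected with date and time, so no new data are needed, provided both assessments are in the database. That should be confirmed first.
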